4.2 SCIENTIFIC RATIONALE FOR STUDY DESIGN

Participants will serve as their own controls in this repeated measures design. This design is ideal for avoiding random effects of individual differences unrelated to the constructs of interest and will provide maximal power for detected control versus target stimulation effects. All participants will be healthy, young adults. This group is ideal for studying normal brain function apart from developmental effects and aging effects and without any confounding effects of disease or disorder.

4.3 JUSTIFICATION FOR INTERVENTION

There are few tools for causally manipulating the cortical balance of excitation to inhibition in humans. TMS was chosen as an intervention for modulating E/I balance in the dorsolateral prefrontal cortex to alter critical dynamics with consequences for working memory and subjective cognitive effort. Transcranial magnetic stimulation has already been shown to modulate cortical E/I balance, with effects on working memory performance when targeting the dorsolateral prefrontal cortex. It is widely used, safe

and effective. While there are pharmacological means of modulating E/I balance, it is impossible to selectively target the dorsolateral prefrontal cortex with pharmacological interventions.

A single train of 600 pulses of continuous theta burst stimulation (cTBS) is a standard cTBS design. We are using a modification involving two trains of 600 pulses separated by 5 to 25 minutes of rest in between based on a meta-analysis showing that the effects are more reliable and more durable for a spaced cTBS design relative to a single train cTBS (Chung et al. 2016).

We will require two separate stimulation sessions for participants so that we can compare the effects of stimulation on the target versus a control location. The sessions will be separated by at least one week providing sufficient time for normalization of brain function between sessions.

Both sessions are needed for a within-participants comparison of target versus control stimulation effects.

4.4 END-OF-STUDY DEFINITION

A participant is considered to have completed the study if he or she has completed the MR scan session, one target stimulation session, and one control session.

The end of the study is defined as completion of the second stimulation session as shown in the Schedule of Activities (SoA), **Section 1.3**.

5 STUDY POPULATION

5.1 INCLUSION CRITERIA

In order to be eligible to participate in this study, an individual must meet all of the following criteria:

1. Provision of signed and dated informed consent form
2. Stated willingness to comply with all study and availability for the duration of the study
3. Males and females; Ages 18-45
4. Healthy, neurologically normal with no diagnosed mental or physical illness
5. Willingness to adhere to the MRI and two session stimulation protocol
6. Fluent in English
7. Normal or corrected to normal vision
8. At least twelve years of education (high school equivalent)
9. Right-handed

Participants will report simply whether they meet screening criteria prior to consent and this data will not be retained. We will only retain data collected after participants give signed written consent and are thus considered enrolled in the study. Participants responding that they do not meet one of the screening criteria will not be enrolled.

5.2 EXCLUSION CRITERIA

An individual who meets any of the following criteria will be excluded from participation in this study:

1. Ongoing drug or alcohol abuse
2. Diagnosed psychiatric or mental illness
3. Currently taking psychoactive medication
4. Prior brain injury
5. Metal in body
6. History of seizures or diagnosis of epilepsy
7. Claustrophobia
8. Pregnant or possibly pregnant
9. Younger than 18 or older than 45
10. Use of medications which potentially lower the usage threshold

Participants younger than 18 are excluded because there is evidence that cortical excitation to inhibition changes throughout childhood and adolescence and has been associated with an increase in critical dynamics with development (Smit et al. 2011). There is also evidence of increasing excitation to inhibition altering scale-free properties linked to critical dynamics in older adults relative to young adults (Voytek et al. 2015). We are restricting our study to young adults aged 18-45 to avoid any confounds associated with early development or cognitive aging.

Participants will be asked if they are pregnant or possibly pregnant and excluded from participation if they affirm either.

5.3 LIFESTYLE CONSIDERATIONS

During this study, participants are asked to:

- Come to the study well-rested
- Refrain from using products in their hair to avoid adversely impacting impedance for EEG recordings
- Avoid high amounts of caffeine intake the morning of the study

5.4 SCREEN FAILURES

Screen failures are defined as participants who consent to participate in this study but are not subsequently assigned to the study intervention or entered in the study. Individuals who do not meet the criteria for participation in this trial (screen failure) because of meeting one or more exclusion criteria that are likely to change over time may be rescreened. Examples include coming back for a stimulation session after receiving a full night's rest, or without products in the participant's hair.

5.5 STRATEGIES FOR RECRUITMENT AND RETENTION

Participants will be recruited via flyers and announcements which detail core inclusion / exclusion criteria. As such we only anticipate needing to recruit around 40 individuals in order to meet our target (30 participants; 15 male / 15 female) recruitment. Flyers will be posted around the Brown University Community, and announcements will be posted in local periodicals (e.g. the Today @ Brown newsletter), which is appropriate for communicating with a sample of young adults in the target age range. This recruitment strategy has proven successful in recruiting participants who match community demographics in prior study and we anticipate it will remain successful going forward.

Potential participants who see our flyers and announcements will be invited to expressing their interest by emailing us. We will respond to this email with a brief description of what is involved in the study and inclusion / exclusion criteria. Our email will also instruct potential participants to simply say that yes they do or do not meet all of the screening criteria (without specifying which criteria they do / do not meet). If they say they meet all criteria, they are invited to a first session for informed consent procedures. After they give consent, they then fill out detailed screening forms which we retain as part of the study record.

Our anticipated enrollment will approximate the demographics of Providence, Rhode Island and the Brown University community including 26 not Hispanic or Latino and 4 Hispanic or Latino participants. Racial breakdown will approximate 2 Asian, 2 Black or African American, 22 White, and 4 More than One Race participants. All participants will be between the ages of 18 and 45.

To increase the chances that participants come to all study sessions, we will describe the procedures in detail during the recruitment and consenting processes, indicating that we are recruiting participants who would be willing to participate in all sessions (though participants can, at any time, decide to no longer participate and there will be no penalty if that happens). We will also send participants a calendar invite to remind them of their participation and a reminder email the day before their session.

Participants will be paid \$20/hour for MRI, or TMS and EEG experiments. Depending on the experiment, participants may have the opportunity to earn additional compensation. Specifically, participants will have

the opportunity to select among offers of money to repeat various levels of the working memory task for money. Based on their choices, participants may receive an additional (\$0.50 to \$4.00) in each experimental TMS sessions. This bonus is part of an experimental design intended to assess how people evaluate the subjective costs of cognitive effort.

Participants in MRI are also given an anatomical picture of their brain in digital format if they desire. Participants will be paid in cash, at the end of each experimental session. For participants completing the three sessions (MRI, active TMS, and control stimulation), their total pay will not exceed \$208 across all three sessions (\$40 for the MRI session, and \$84 each for the TMS sessions).

We do not believe these nominal amounts to be coercive and moreover will inform participants that they can end their participation in the experiment at any time, and they will receive a pro-rated amount of remuneration for their time in the respective session.

6 STUDY INTERVENTION(S) OR EXPERIMENTAL MANIPULATION(S)

6.1 STUDY INTERVENTION(S) OR EXPERIMENTAL MANIPULATION(S) ADMINISTRATION

6.1.1 STUDY INTERVENTION OR EXPERIMENTAL MANIPULATION DESCRIPTION

The study intervention is modulation of cortical excitation to inhibition (E/I) balance in the dorsolateral prefrontal cortex (dlPFC) by means of 2 trains of spaced continuous theta burst stimulation (cTBS) using a transcranial magnetic stimulation device. As prior work (Huang et al 2005; Chung et al. 2018) has shown that cTBS reliably decreases the cortical E/I ratio with diverse cortical targets, we expect to replicate a reduction in E/I balance when applied to the dlPFC. The mechanism of action is thought to be an increase in inhibitory neurotransmission across diverse timescales. The endpoint of this stimulation will be a decrease in the local E/I ratio that should last at least 60 minutes post-stimulation (Chung et al., 2018).

We will assess the change in E/I balance by quantifying the functional E/I ratio as previously done in a study of the GABA receptor agonist Zolpidem (Bruining et al. 2020). We furthermore anticipate that a reduction in dlPFC E/I balance will also make the dynamics of dlPFC neurons more sub-critical (Pfeffer et al. 2018; Poil et al. 2012), hence we will test the prediction that cTBS weakens long-range temporal correlations otherwise found in the brain in a critical state. Moreover, we will test the prediction that cTBS to the dlPFC will undermine working memory performance and amplify subjective effort, given the role of the dlPFC in working memory processes.

Importantly, we will contrast the effects of dlPFC cTBS with control cTBS to the angular gyrus. Active stimulation of a control region is preferable to sham stimulation since the latter is less convincing than active control stimulation and may present a confound of participant awareness. Also, the angular gyrus is a suitable control region because, unlike the dlPFC, it is not part of the frontoparietal or dorsal attention networks which have been implicated in working memory and cognitive control (Power et al. 2011) and moreover has a low participation coefficient indicating that it is minimally coupled with these networks (Power et al. 2013).

6.1.2 ADMINISTRATION AND/OR DOSING

As noted, the intervention is spaced, cTBS to either (in alternate sessions) the anatomically-defined dlPFC or angular gyrus. Each session will thus entail two trains of 50 Hz triplet bursts of stimulation delivered at 5 Hz (theta rhythm) continuously for 40 seconds (600 pulses for each train for a total of 1200 pulses) at an intensity based on 80% of a participant's active motor threshold to either the target or control region. These two trains will thus constitute the full-dose intervention in either location.

Each participant will have their own personal set of two sessions and will thus not interact with other participants during the study.

6.2 FIDELITY

6.2.1 INTERVENTIONIST TRAINING AND TRACKING

All TMS operators will receive training on the two key variables which may affect the consistency of cTBS. The first is the strength of stimulation intensity. Here, stimulation intensity will be based on participants' active motor threshold, which is diagnosed with the use of TMS-evoked potentials measured by electromyography and leads attached to participants' right hand, pursuant to a single pulse to their motor cortex hand knob. Motor thresholding will be based on a semi-automated threshold detection algorithm which is given feedback about the efficacy a given pulse for eliciting a motor evoked potential of 100 microvolts from peak to trough. Thus threshold identification should be standardized across participants, as should corresponding stimulation intensities.

The second degree of freedom is the precision of TMS targeting. For both motor threshold detection and cTBS, it is important to ensure precise targeting (of the hand knob and dlPFC, respectively). To ensure consistent targeting, we will use participant-specific structural MRI scans coupled with 3D vision-based neuronavigation systems. The neuronavigation system gives real-time feedback for precision targeting. Also, the exact location of every single pulse is recorded during stimulation, to ensure consistency. Finally, only two TMS operators will be used for the entirety of the study (the PI and one assistant), and both will be thoroughly trained to ensure consistent administration.

6.3 MEASURES TO MINIMIZE BIAS: RANDOMIZATION AND BLINDING

All participants will complete both one target and one control stimulation session, but the order of these sessions will be pseudo-randomized. Specifically, participants will be assigned participant ID numbers based on their order of recruitment, but the participant ID numbers will be pseudo-randomized with respect to the order of target versus control stimulation sessions. Pseudo-randomization of IDs will be saved in a digital file and included in all subsequent analyses as a covariate of no interest. Any breaking of pseudo-randomization will be corrected with subsequent re-pseudo-randomization of unassigned ID numbers to ensure balance in session orders across participants. This pseudo-randomization will be managed / maintained by the PI.

The specific session that a participant is in (target versus control region) will be known to the experimenter (there is no way for the experimenter not to know since they are administering stimulation). To mitigate the impact on participants, they will be instructed that we will stimulate the brain on two different days, making no reference to possible differential effects across brain regions. The experimental condition will not be explained to the participant until the end of their participation, during debriefing.

Any instance of accidental unblinding – e.g. the participant learns that dlPFC stimulation is considered target, and angular gyrus is considered control stimulation will be noted and subsequent analysis will be conducted both including and excluding these participants to ensure that their inclusion has no effect on the conclusions of the study.

While it may be possible for some participants to infer that effects of stimulation at different sites should have differential effects, they will not be made aware which sites we expect to impact on working memory performance or subjective effort.

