Test whether continuous theta-burst stimulation decreases E/I balance	Decrease in the functional E/I (fE/I) balance ratio at rest, estimated from EEG data after TMS	The fE/I measure derived from EEG activity has been shown to index E/I balance in silico, and in vivo with humans taking GABAergic medication. Thus, in principle, a change in E/I balance induced by TMS should also be apparent in the EEG dynamics and thereby the fE/I of channels near the stimulation site. Changes in fE/I should moderate effects of theta-burst stimulation on critical dynamics and	Theta-burst stimulation is thought to promote inhibitory neurotransmission, at diverse timescales, thus decreasing E/I balance in local microcircuits. The fE/I measure should be sensitive to these neuromodulatory changes.
Control for session order effects on task performance, subjective effort.	Effects of session order on accuracy (d') and reaction times in working memory task, on	Session order will be included as a covariate in all analyses since participants improve discrimination accuracy and response	Practice improves performance, and people find tasks with which they have more practice

OBJECTIVES	ENDPOINTS	JUSTIFICATION FOR ENDPOINTS	PUTATIVE MECHANISMS OF ACTION
	discounting of rewards as a function of subjective effort.	speed across sessions with the working memory task. In turn, they find tasks to be less effortful across sessions.	to be subjectively easier.
Tertiary/Exploratory			

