4 STUDY DESIGN

4.1 OVERALL DESIGN

The hypothesis to be studied in this Trial is that criticality in the brain depends on the balance of cortical excitation to inhibition and that sub-criticality impacts on working memory and subjective cognitive effort. This hypothesis leads to predictions including that TMS protocols which decrease the cortical excitation to inhibition ratio (like theta burst stimulation) will make the brain more sub-critical. In turn, when theta-burst stimulation is targeted at regions involved in working memory like the dorsolateral prefrontal cortex, this predicts worse, more inflexible working memory performance and greater subjective effort when people are engaged in working memory tasks.

We will use a repeated measures design wherein every subject is their own control. Specifically, on different days, separated by at least one week, participants will receive continuous theta burst stimulation to either their dorsolateral prefrontal cortex (the active condition) or the angular gyrus (the control condition). The order of these sessions is pseudo-randomized across participants. Specifically, 15 of our target 30 participants will be randomly pre-assigned to complete an active condition session first and control condition second and vice versa for the other 15 participants. The pre-assignment will be determined by permutation of a list of subject numbers before recruitment starts. Every subject number will subsequently be assigned to participants in order of their recruitment. Errors in randomization will be documented and session order will be included as a covariate in all analyses.

Participants will come in for three sessions: 1) a first session to complete paperwork and an MRI structural scan for subsequent neuronavigation and a resting state scan, 2) one counterbalanced order session for dorsolateral prefrontal cortex stimulation and working memory task performance and 3) another counterbalanced order session for angular gyrus stimulation and working memory task performance. The first stimulation session can happen the day after an MR scan (but no more than 113 days after the MR

scan) and the second stimulation session can happen one week after the first stimulation session (but no more than 113 days after the first stimulation session).

This is a single-site trial.

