9.2 SAMPLE SIZE DETERMINATION

While studies on the effects of continuous theta-burst stimulation (cTBS) on critical dynamics have never been conducted, power calculations are based on prior work showing that cTBS can alter E/I balance and working memory function. Specifically, Schicktanz et al. (2015) found that a single train of cTBS to the left dorsolateral prefrontal cortex reduced N-back task accuracy (the same working memory task we will use in the present study) with an effect size on accuracy of $d = 1.39$, 3–21 minutes post-stimulation. This performance effect was established for the 2-back which is our mid-difficulty level. Using g*Power (Faul et al., 2007), we estimate that if the true effect size remains the same, we will have a 95% chance of detecting a cTBS effect on 2-back performance with 30 participants at $p < 0.05$. Importantly, with 30 participants, we will still have 80% power to detect a group difference in performance even if the true

effect size is less than half as large ($d = 0.53$). As such, our target recruitment is set at 30 participants (but will run additional to reach 30 complete participant-session sets, as needed, due to drop-out).

While effect sizes can vary in cTBS owing to considerable inter-individual differences in response to stimulation, we are taking additional measures to reduce reliability including participant-specific brain images and neuronavigation, and also the use of two, rather than one train of cTBS. As such, if anything, we expect the prior estimates to be a lower bound on what we observe.

While this estimate is based on working memory performance alone, this outcome is arguably the most important because it is the one measure that has been linked with E/I balance, with subjective effort, and with critical dynamics in other studies. As such, this measure was selected because it is also informative about all primary and secondary outcomes.

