9.4 STATISTICAL ANALYSES

9.4.1 GENERAL APPROACH

There are no categorical outcomes. Key measures are all continuous outcomes, and are described in detail in the next section. They will be analyzed according to pre- versus post-stimulation means. We will also report standard errors for each outcome. Key outcomes have multiple associated measures. Multiple measures will be used to assess reliability by parallel forms.

We will use standard frequentist cut-offs of $p < 0.05$ for all statistical tests, correcting for multiple comparisons. Key t-tests will include pre-post distinctions in E/I balance measures, working memory performance measures, and measures of criticality.

Covariates of no interest to be included are sex and age which we will incorporate via multiple regression to ask whether cTBS alters key outcomes (described in the next session).

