9.4.2 ANALYSIS OF THE PRIMARY ENDPOINT(S)

The following key outcomes will be assessed in this study. All measures are interval with the exception of the categorical covariate of sex.

- Subjective effort
 - Likert scale ratings (ranging from 1-10) of task-induced effort, demand, time pressure, and stress
 - subjective values as estimated from an indifference point discounting procedure
 - self-reported motivation to engage in demanding tasks on a set of Likert scales with continuous values ranging from 0-20
- E/I balance
 - fEI derived measure with exponents ranging approximately from 0.0-2.0
 - power-law exponents with exponents approximating -2.0
- Critical dynamics
 - Long range temporal correlations – a derived measure with exponents ranging approximately from 0.5-1.0
 - Avalanche size and duration distribution exponents approximating -2.0 and -1.5, respectively
- N-back working memory performance
 - overall accuracy rate as a percentage
 - median correct reaction times by trial type: lures versus targets versus regular trials
 - the discrimination index d'

Primary analyses of these outcomes will entail multiple regression models in which outcomes will be regressed on cTBS condition (target versus sham), controlling for sex and age.

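### Section 6.3 defines the session-order covariate as the assigned sequence, which as a main effect in the condition model leaves the practice effect in the error; session number is the term needed

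*Protocol*

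**What the plan says.** Each participant has one dlPFC (target) and one angular gyrus (control) session. Section 4.1 fixes the orders in advance: "15 of our target 30 participants will be randomly pre-assigned to complete an active condition session first and control condition second", with the reverse for the other 15. It then promises session order as a covariate without giving a coding.

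Section 6.3 comes closest to a definition. It ties the order to the participant number and says: "Pseudo-randomization of IDs will be saved in a digital file and included in all subsequent analyses as a covariate of no interest". Section 3 gives the reason for the covariate: "Session order will be included as a covariate in all analyses since participants improve discrimination accuracy and response" speed across sessions. It also lists effects of session order as a secondary endpoint, with practice as the mechanism.

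Section 9.4.2 states the primary model: "outcomes will be regressed on cTBS condition (target versus sham), controlling for sex and age". It contains no order or session term and no participant term. The opening of Section 9 says there will be no formal SAP, so the protocol is the only planned place for the definition.

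**The concern.** Two different variables go by the name session order. Sequence (target first or control first) is constant across a participant's two sessions. Session number (first or second) changes within the participant. Practice, the stated reason for the covariate, is a shift between a participant's own two sessions, so it is a session-number effect. An analyst who follows 6.3 literally and adds sequence to the 9.4.2 regression would believe practice had been handled when it had not.

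At stake is the precision of the dlPFC-versus-angular-gyrus contrast for working memory and subjective effort, the outcomes for which Section 3 expects practice. If the completed orders drift from balance, some bias is at stake too.

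**Working it through.** **Inputs.** From the protocol: 30 participants (9.2, "our target recruitment is set at 30 participants"); 15 per order (4.1); significance level 0.05 (9.4.1), taken as two-sided because no sidedness is stated; d = 0.53 with 80% power (9.2). Assumed: a practice effect p of 0.25 to 1.0 SD of the target-minus-control difference, where the SD is net of practice, and a participant effect in the model.

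**The plan's own figure.** Section 9.2 says: "with 30 participants, we will still have 80% power to detect a group difference in performance" at d = 0.53. A paired t-test with n = 30, two-sided 0.05, has noncentrality 0.53 × √30 = 2.90 and power 0.801. The 80% is reproduced and implies a paired analysis.

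**Why a sequence main effect does nothing here.** Code condition c = ±½ (target +½), session t = ±½ (second +½) and sequence s = ±1 (target first +1). Then t = −s·c. Within each participant both c and t sum to zero while s is constant, so s is orthogonal to c and to t at any split. The practice effect lies wholly in t, and s cannot absorb it.

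With a noise-free practice effect of 1 unit at 15/15, the residual sum of squares is:

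- condition only: 15.0
- condition + sequence: 15.0
- condition + session number: 0
- condition × sequence: 0
- target-minus-control differences, no covariate: 30; regressed on sequence: 0

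In one simulated data set (15/15, mixed model with a random participant effect), the condition estimate was −0.0897 in every model. Its standard error was 0.1841 without sequence, 0.1841 with sequence and 0.1321 with session number.

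**Power.** The paired difference is D = τ − p·s + e, with SD(e) = 1. If practice is left in, SD(D) at 15/15 is √(1 + p²), so the standard error is inflated by that factor and the effective d is 0.53/√(1 + p²).

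| p | √(1 + p²) | effective d | power, noncentral t | power, simulated | type I error, simulated |
|---|---|---|---|---|---|
| 0 | 1.00 | 0.530 | 0.801 | 0.805 | 0.050 |
| 0.25 | 1.03 | 0.514 | 0.777 | 0.787 | 0.043 |
| 0.5 | 1.12 | 0.474 | 0.709 | 0.730 | 0.028 |
| 0.75 | 1.25 | 0.424 | 0.612 | 0.637 | 0.014 |
| 1.0 | 1.41 | 0.375 | 0.510 | 0.506 | 0.006 |

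The simulations used 40,000 trials per setting. The closed form is approximate, because a fixed ±p shift is not normal noise; the two agree within 3 points. A repeat with 200,000 trials gave power of 0.782, 0.725, 0.628 and 0.501 for p = 0.25 to 1.0, so the simulated figures are good to about one point. With session number in the model (28 degrees of freedom), power is 0.80 and type I error about 0.05 at every p.

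**Bias.** The size of the bias left in the condition estimate is p × (n1 − n2)/30, where n1 and n2 are the numbers completing each order:

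- 15/15: 0
- 16/14: 2/30 = 6.7% of the practice effect
- 17/13: 4/30 = 13.3%
- 18/12: 6/30 = 20%, or 0.05, 0.10 and 0.20 SD for p = 0.25, 0.5 and 1.0

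Session number removes the bias at every split tried.

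**The case against.** **The definition is not settled.** Only 6.3 points clearly to sequence. Section 3 speaks of improvement across sessions, and 4.1 describes both target stimulation coming first or second and the tasks being done first or second. Someone who read session order as session number throughout would fit the right model. This stands: the document is ambiguous, and it does not commit to the wrong coding in every section.

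**Sequence can work.** A reader might infer that the promised covariate can never remove practice. That is too strong. Regressing target-minus-control differences on the same sequence variable, or letting it interact with condition, removes practice completely. The fault needs a main effect in a regression of session outcomes on condition. That is the form 9.4.2 suggests, but it does not spell out the row structure.

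**Counterbalancing protects the estimate.** A reader might also infer a biased contrast. At 15/15 the bias is zero, and 6.3 provides for re-randomizing unassigned numbers to keep balance. No unbalanced split is planned. However, 7.2 replaces withdrawn participants without saying that the replacement takes over the same order, so exact balance among completers is not guaranteed.

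**The secondary endpoint.** It is tempting to say that it would compare the two order groups and so miss practice. No section says so, and the session 1 to session 2 change is the natural reading. Only a clarifying sentence is needed.

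**The power loss rests on assumptions.** No practice effect size is given. At 0.25 SD the loss is small. If d = 0.53 is scaled to an SD that already includes practice, the unadjusted paired test keeps its 80%; session number would still reduce the standard error by the factor in the table. The error is conservative, and the E/I and criticality predictions in 9.1 are made against pre-stimulation rest, so they are less affected.

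**Conclusion.** The point holds as a fault of definition with a cost in precision. Section 6.3 describes sequence, and Section 3 needs session number. Entered as a main effect in the 9.4.2 regression with a participant effect, the variable in 6.3 does not do the job Section 3 gives it.

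At 15/15 the estimate is unbiased and the test conservative. Power drops from 80% to about 79%, 73%, 64% and 51% across the assumed practice range. This rests on three assumptions the protocol does not supply: the practice range, d = 0.53 scaled to the SD net of practice, and a participant term. Bias is conditional on imbalance and equals the practice effect times (n1 − n2)/30. The documents do not support saying that the covariate could never work, that the planned contrast is biased, or that the secondary endpoint will be tested by comparing order groups.

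Restoring session order to 9.4.2 in the sense of 6.3 would not cure the problem; the definition has to change too.

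**What to change.** - In Section 3, 4.1, 6.3 and 9.4.2, define the covariate as session number (1 or 2), entered as a within-participant fixed effect with condition and a participant effect. Add it to the covariates listed in 9.4.1, which names only sex and age.
- Equivalently, specify a regression of target-minus-control differences on order coded +1/−1, with the condition effect tested as the intercept. The ±1 coding matters, because under 0/1 coding the intercept would be the effect in one order group only.
- State in Section 3 that the session-order secondary endpoint is the change from session 1 to session 2.

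The cost is wording and one degree of freedom (28 in place of 29). Session number is already known for every visit, so no new data are needed.
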